Clinical Trial Protocol: Study PRM-151-202

Study Title: A Phase 2 Trial to Evaluate the Efficacy of PRM-151 in Subjects with Idiopathic Pulmonary Fibrosis (IPF)
Study Number: PRM-151-202
Study Phase: 2
Product Name: PRM-151
IND Number: 110,774
EUDRACT Number: 2014-004782-24
Indication: Idiopathic Pulmonary Fibrosis (IPF)

Sponsor: Promedior, Inc
[name]
[name]
[contact]
[contact]

Sponsor Contact: [REDACTED]
Medical Director: [REDACTED]
Medical Monitor: [REDACTED]

	Date
Original Protocol:	Version 1.0 11 November 2014
Amendment # 1:	Version 2.0 26 February 2015
Amendment # 2:	Version 3.0 11 March 2015
Amendment # 3:	Version 4.0 3 February 2016

Confidentiality Statement

The information contained herein is confidential and the proprietary property of Promedior, Inc and any unauthorized use or disclosure of such information without the prior written authorization of Promedior is expressly prohibited.

SYNOPSIS

Sponsor: Promedior, Inc
Name of Finished Product: Recombinant human Pentraxin-2; PRM-151
Study Title: A Phase 2 Trial to Evaluate the Efficacy of PRM-151 in Subjects with Idiopathic Pulmonary Fibrosis (IPF)
Study Number: PRM-151-202
Study Phase: Phase 2
Investigational Product; Dose; and Mode of Administration: PRM-151 10 mg/kg every 4 weeks via intravenous infusion over 60 minutes. On all dosing days, dosing will occur after all safety and efficacy assessments scheduled for that visit are completed.
Comparator Dose; and Mode of Administration: Placebo will be administered via IV infusion over 60 minutes.
Primary Objective: 
 Determine the effect size of PRM-151 relative to placebo in change from Baseline to Week 28 in mean FVC% predicted, pooling subjects on a stable dose of pirfenidone or nintedanib with subjects not on other treatment for IPF.
Secondary Objective(s): 
 Determine the effect size of PRM-151 relative to placebo in change from Baseline to Week 28 in normal lung parenchyma as quantified on high- resolution CT (HRCT) imaging analysis, pooling subjects on a stable dose of pirfenidone or nintedanib with subjects not on other treatment for IPF. Determine the effect size of PRM-151 relative to placebo in change from Baseline to Week 28 in mean FVC% predicted, separately in subjects on a stable dose of pirfenidone or nintedanib and separately in subjects not on other treatments for IPF. Determine the effect size of PRM-151 relative to placebo in change from Baseline to Week 28 in normal lung parenchyma as quantified on HRCT imaging analysis, separately in subjects on a stable dose of pirfenidone or nintedanib and in subjects not on other treatments for IPF. Assess the tolerability and safety of PRM-151 in subjects with IPF through Week 28 Assess the ability of PRM-151 to reduce disease-related events associated with mortality. Determine the effect size of PRM-151 relative to placebo on pulmonary function in addition to mean change in FVC% predicted. Determine the effect size of PRM-151 relative to placebo on 6-minute walk distance. Assess the effect size of PRM-151 relative to placebo on Hb-corrected DLCO.

Study Endpoints:**Primary:**

- The primary endpoint is the mean change in FVC % predicted from Baseline to Week 28.

Secondary:

- **Structural Imaging:**

- Mean change from Baseline to Week 28 in total lung volume and volume of parenchymal features on HRCT (in ml and % of total lung volume) representative of interstitial lung abnormalities (ILA) including ground glass density, reticular changes, and honeycombing, using quantitative imaging software.
- Mean change from Baseline to Week 28 in volume of parenchymal features on HRCT (in ml and % of total lung volume) representative of normal lung (non-ILA), including normal and mild low attenuation areas, using quantitative imaging software.
- Correlation between mean change from Baseline to Week 28 in FVC % predicted and mean change from Baseline to Week 28 in total lung volume and volume of parenchymal features on HRCT (in ml and % of total lung volume) representative of interstitial lung abnormalities (ILA), including ground glass density, reticular changes, and honeycombing by quantitative imaging software.

- **Safety:** Tolerability/safety will be assessed over the 28-week study period by the following parameters:

- Incidence of AEs.
- Incidence of serious adverse events (SAEs).
- Incidence of respiratory AEs and SAEs.
- Proportion of subjects discontinuing study drug due to AEs.
- Change from Baseline in hematology and serum chemistries.
- All-cause mortality.
- Mortality due to respiratory deterioration.

- **Disease related events associated with mortality:** The number of “respiratory decline” events over the 28-week study period as defined below:

- Unscheduled visits to a healthcare professional for respiratory status deterioration.
- Urgent care visits for respiratory status deterioration.
- Hospitalization due to a worsening or exacerbation of respiratory symptoms.

All “respiratory decline” events will be further characterized according to the definitions of IPF-related acute exacerbation, as proposed by an expert committee sponsored by the IPF Clinical Research Network and the National Heart Lung and Blood Institute (NHLBI) (Collard, Moore et al. 2007) and applied by (Collard, Yow et al. 2013)

- Acute onset of symptoms (< 30 days in duration)
- New radiographic abnormalities (bilateral ground glass or consolidation on HRCT with no pneumothorax or pleural effusion)
- The absence of an identified infectious etiology by routine clinical practice

- Exclusion of alternative causes by routine clinical practice, including:
 - a. Left heart failure
 - b. Pulmonary embolism
 - c. Identifiable cause of acute lung injury
- **Pulmonary Function Tests**
 - Proportion (%) of subjects with a decline in FVC% predicted of $\geq 5\%$ and $\geq 10\%$ from Baseline to Week 28.
 - Proportion (%) of subjects with a decline in FVC in ml of ≥ 100 ml and ≥ 200 ml from Baseline to Week 28.
 - Proportion of subjects with an increase in FVC % predicted of $\geq 5\%$ and $\geq 10\%$ from Baseline to Week 28.
 - Proportion of subjects with an increase in FVC in ml of ≥ 100 ml and ≥ 200 ml from Baseline to Week 28.
 - Proportion of subjects with stable disease by FVC %, defined as a change in FVC % predicted of $< 5\%$ from Baseline to Week 28.
 - Proportion of subjects with stable disease by FVC in ml, defined as a change in FVC of < 100 ml from Baseline to Week 28.
 - Mean change from Baseline to Week 28 in % predicted Hb-corrected diffusion capacity of carbon monoxide (DLCO).
 - Change in 6-minute walk distance, in meters, from Baseline to Week 28.

Exploratory:

- **Other Weeks**
 - Examine the change from Baseline at Weeks 4, 8, 12, 16, 20, 24 and 28 for the FVC % predicted, FVC in ml, and 6MWT distance
- **Structural Imaging**
 - Transitions from Baseline to Week 28 between all categories of lung features (normal, ground glass density, reticular changes, honeycombing, and mild, moderate, and severe low attenuation areas) by quantitative imaging software.
 - Correlation of transitions between categories of lung features by quantitative imaging and changes in FVC% predicted.
 - Correlation of transitions between categories of lung features by quantitative imaging and changes in Hb-corrected DLCO.
 - Impact of inspiratory effort on results of HRCT quantitative imaging.
- **Patient Reported Outcomes**
 - Change in Patient Reported Outcomes as measured by King’s Brief Interstitial Lung Disease Questionnaire (K-BILD) and Leicester Cough Questionnaire (LCQ) from Baseline to Week 28.
- [REDACTED]
- [REDACTED]
- [REDACTED]
- [REDACTED]

Study Design:

This study is a Phase 2, randomized, double-blind, placebo controlled, pilot study designed to evaluate the efficacy and safety of PRM-151 administered through Week 24 to subjects with

IPF. Subjects meeting the eligibility criteria for the study will be randomized with a 2:1 ratio to PRM-151 at a dose of 10 mg/kg every 4 weeks or placebo. The randomization will be stratified according to other treatments for IPF (subjects receiving pirfenidone or nintedanib and subjects with no other treatment for IPF, with a minimum of 25% of subjects on no other treatment). Efficacy will be evaluated through pulmonary function tests (PFTs) including spirometry, Hb-corrected Diffusion Capacity (DLco) and Total Lung Capacity by Nitrogen washout method, quantitative imaging analysis of high resolution CT (HRCT), 6-minute walk test (6MWT), and subject reported outcomes (PROs).

Subjects will be evaluated for study eligibility during Screening within 4 weeks before enrollment and Baseline assessments. Subjects who are determined to be eligible, based on Screening assessments, will be enrolled in the study and randomly allocated to treatment with PRM-151 or placebo. Subjects will receive study drug treatment for at least 24 weeks.

Approximately 117 subjects will be randomly assigned on a 2:1 basis to treatment with PRM-151 or placebo, as follows:

- PRM-151 10 mg/kg IV infusion over 60 minutes days 1, 3, and 5, then one infusion every 4 weeks
- Placebo IV infusion over 60 minutes on days 1, 3, and 5, then one infusion every 4 weeks

After completion of study treatment through Week 24, all subjects may receive PRM-151 10 mg/kg IV infusion over 60 minutes Days 1, 3, and 5, then once every 4 weeks for an indefinite period of time in an open label study extension. Dosing on Days 1, 3 and 5 will be repeated once every 28 weeks.

Study Duration:

Subjects will receive study drug for a minimum of 24 weeks.

Subjects will participate in the study for an indefinite period of time, including a 4-week screening period, 24-week treatment period, and an open-label treatment extension period, and a 4-week follow up visit.

Study Inclusion and Exclusion Criteria:

Inclusion Criteria:

1. Subject is aged 40-80 years.
2. Subject has IPF satisfying the ATS/ERS/JRS/ALAT diagnostic criteria (Raghu, Collard et al. 2011).

In the absence of a surgical lung biopsy, HRCT must be “consistent with UIP” defined as meeting either criteria A, B, and C, or criteria A and C, or criteria B and C below:

- A. Definite honeycomb lung destruction with basal and peripheral predominance.
 - B. Presence of reticular abnormality AND traction bronchiectasis consistent with fibrosis, with basal and peripheral predominance.
 - C. Atypical features are absent, specifically nodules and consolidation. Ground glass opacity, if present, is less extensive than reticular opacity pattern.
3. If on pirfenidone or nintedanib, subject must have been on a stable dose of pirfenidone or nintedanib for at least 3 months prior to screening without increase in

FVC% predicted on two consecutive PFTs, including screening PFTs. Subjects may not be on both pirfenidone and nintedanib.

4. If not currently receiving pirfenidone or nintedanib, subject must have been off pirfenidone or nintedanib for ≥ 4 weeks before baseline.
5. Subject has a FVC $\geq 50\%$ and $\leq 90\%$ of predicted.
6. Subject has an Hb corrected and/or Hb uncorrected $DL_{CO} \geq 25\%$ and $\leq 90\%$ of predicted.
7. Minimum distance on 6MWT of 150 meters.
8. Subject has a forced expiratory volume in 1 second (FEV_1)/FVC ratio > 0.70 .
9. Women of child bearing potential (WCBP), defined as a sexually mature woman not surgically sterilized or not post-menopausal for at least 24 consecutive months if ≤ 55 years or 12 months if > 55 years, must have a negative serum pregnancy test within four weeks prior to the first dose of study drug and must agree to use highly effective methods of birth control throughout the study. Highly effective methods of contraception include combined (estrogen and progestogen containing) hormonal contraception associated with inhibition of ovulation by oral, intravaginal, or transdermal administration; progestogen-only hormonal contraception associated with inhibition of ovulation by oral, injectable, or implantable administration; intrauterine device (IUD); intrauterine hormone-releasing system (IUS); bilateral tubal occlusion; partner vasectomy, and total abstinence (only if total abstinence is the preferred method and usual lifestyle of the subject). Adequate contraceptive use should be continued until 28 days after the final dose of the study drug.
10. Subject has a life expectancy of at least 9 months
11. Subject, according to the investigator's best judgment, can comply with the requirements of the protocol.
12. Subject and the treating physician considered all medicinal treatment options and / or possibly a lung transplantation prior to considering participation in the study. If the subject is on a lung transplant list, the investigator anticipates the subject will complete the study prior to transplant.
13. Subject has provided written informed consent to participate in the study.

Exclusion Criteria:

1. Subject has emphysema $\geq 50\%$ on HRCT or the extent of emphysema is greater than the extent of fibrosis according to reported results from the most recent HRCT.
2. Subject has a history of cigarette smoking within the previous 3 months.
3. Subject has received investigational therapy for IPF within 4 weeks before baseline.
4. Subject is receiving systemic corticosteroids equivalent to prednisone > 10 mg/day or equivalent within 2 weeks of baseline.
5. Subject received Immuno-suppressants (e.g. azathioprine, cyclophosphamide, or cyclosporine or other immunosuppressants including those used after organ transplant) within 4 weeks of baseline. Subject has a history of a malignancy within the previous 5 years, with the exception of basal cell skin neoplasms. In addition, a malignant diagnosis or condition first occurring prior to 5 years must be considered cured, inactive, and not under current treatment.

time. All subjects will receive PRM-151 10 mg/kg IV Days 1, 3, 5 and every 4 weeks in the extension. Dosing on Days 1, 3 and 5 will be repeated once every 24 weeks in the extension. PROs, PFTs, and 6MWT will be done every 4 weeks for the first 24 weeks and then every 12 weeks and DLco, FRC & TLC by nitrogen washout method and HRCT will be done at 1.5 years (Week 76) and 2.5 years (Week 128).

Safety Assessments:

Treatment Period: Tolerability/Safety-Related Assessments

Safety will be evaluated from reported adverse events (AEs), scheduled physical examinations, vital signs, and clinical laboratory test results. Adverse events and concomitant medications will be assessed at all study visits. In addition, information regarding hospitalizations, emergency department visits, and unscheduled or urgent care visits to a health care provider due to a deterioration in respiratory status or symptoms will be collected at all study visits.

Statistical Methods:

The primary analysis is planned after last subject completed W28 assessment. Continuous variables will be summarized by dose group with descriptive statistics (e.g., number of observations, number of missing observations, mean, SD, median, interquartile range, maximum, and minimum). Categorical variables will be tabulated by frequency of subjects per dose group, and percentages will be calculated using the number of available observations as the denominator (i.e. excluding missing values). Efficacy evaluations will be performed using the Full Analysis Set (FAS), defined as all subjects with a Baseline and at least 1 post-Baseline observation for the primary efficacy endpoint. A per-protocol analysis will also be carried out on the Per Protocol (PP) set, a subset of the FAS composed of all subjects treated with the IMP, having received at least the planned IMP infusions on days 1, 3, 5, and weeks 4, 8 and 12 and who did not present any major protocol deviations.

The per-protocol set will be used for secondary analyses of the primary efficacy criterion and for the analysis of some selected secondary efficacy criteria. Safety evaluations will be based on the Safety Population, defined as all subjects who receive at least 1 dose of study drug and have a post-Baseline safety observation. Demographic data will be summarized for all subjects entering the study, and if material differences exist, for the FAS and Safety analysis datasets. (Additional details will be included in the SAP.)

This study is randomized with a 2:1 randomization ratio. A central randomization system will be used. The randomization will be stratified according to the subject's baseline treatment status: baseline pirfenidone or baseline nintedanib or no other therapy for IPF at baseline. The randomization system will also ensure that at least 25% of the subjects in the final study population are on no other therapy for IPF at baseline.

The comparison of PRM-151 with placebo will be carried out via 2-sided statistical tests at alpha=0.10. The primary endpoint will be tested with analysis of variance (ANOVA), with change from Baseline to week 28 in FVC% predicted as dependent variable (outcome), and treatment and stratum, as explanatory variables. FVC% predicted will also be analyzed separately for each level of the stratum variable (in subjects on a stable dose of pirfenidone or nintedanib and in subjects not on other treatments for IPF) using analysis of variance

(ANOVA), with change from Baseline to week 28 in FVC% predicted as dependent variable (outcome), and treatment as the explanatory variable. In case of missing Week 28 assessment of FVC% predicted, the last available observation will be carried forward.

A similar analysis will be done for the secondary and exploratory endpoints, replacing FVC % predicted with the other endpoints as appropriate. Analyses over time will use a three-way ANCOVA with time (nominal study week) as the third factor, including all interactions. The analysis will adjust for correlated errors over time.

For all secondary and exploratory efficacy endpoints, the analyses will be based on observed data only; no data will be imputed.

AEs will be coded by using the most current version of Medical Dictionary for Regulatory Activities (MedDRA) and summarized by system organ class, preferred term, and treatment group for the number and percent of AEs reported, the number of subjects reporting each AE, and the number of subjects with any AE. A by-subject AE data listing including onset and resolution dates, verbatim term, preferred term, treatment, severity, relationship to treatment, action taken, and outcome will be provided.

Safety data, including laboratory evaluations and vital signs assessments, will be summarized by time of collection and by treatment group. In addition, change from Baseline to any post-dose values will be summarized for vital signs and clinical laboratory results. The frequency of subjects with abnormal safety laboratory results will be tabulated by treatment.

Sample Size Considerations:

The primary objective is not to formally demonstrate the superiority of PRM-151 over placebo, but to provide a reliable estimate of the size of the effect of PRM-151 on change from baseline to 28 weeks in mean FVC% predicted, hereafter referred to as the primary endpoint. Nevertheless, the sample-size has been calculated to ensure a sufficient power to demonstrate the efficacy of PRM-151 over placebo on the primary endpoint under a set of hypotheses on effect sizes in the two groups and on the variability of the primary endpoint. The primary endpoint will be tested in a model taking into account the stratification variable (two types of subjects: subjects on a stable dose of pirfenidone, and subjects not on other treatment for IPF).

The sample size calculation is based on the following assumptions:

- Primary endpoint is normally distributed.
- Homogeneity of variance, i.e. the standard deviation is the same in both arms, and for both types of subjects.
- Randomization ratio PRM-151: placebo equals 2:1.
- Expected value of the primary endpoint for subjects on pirfenidone or nintedanib will be -1.5.
- Expected value of the primary endpoint for subjects on no other treatment will be -3.
- Expected value of the primary endpoint for subjects on PRM-151 will be ≥ 0.75 .
- Standard deviation of the primary endpoint is 5.
- 75% of subjects will be on a stable dose of pirfenidone or nintedanib.

- 25% of subjects will not be on other treatment for IPF.
- Significance level (α) = 0.10.
- Desired power to demonstrate superiority is 80%.

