4. INVESTIGATIONAL PLAN

4.1. Overall Study Design and Plan

The current study is a Phase 2, randomized, double-blind, placebo-controlled, pilot study designed to evaluate the efficacy and safety of PRM-151 administered through Week 24 to subjects with IPF. Subjects meeting the eligibility criteria for the study will be randomized to PRM-151 10 mg/kg every 4 weeks or placebo. Efficacy will be evaluated through pulmonary function tests (PFTs), high resolution CT (HRCT), 6-minute walk test (6MWT), and Patient Reported Outcomes (PROs).

Subjects will be evaluated for study eligibility during Screening within 4 weeks before enrollment and Baseline assessments. Subjects who are determined to be eligible, based on Screening assessments, will be enrolled in the study and randomly allocated to treatment with PRM-151 or placebo. Subjects will receive study drug treatment for 24 weeks.

Approximately 117 subjects will be randomly assigned on a 2:1 basis to treatment with PRM-151 or placebo, as follows:

- PRM-151 10 mg/kg IV infusion over 60 minutes on days 1, 3, and 5, then one infusion every 4 weeks
- Placebo IV infusion over 60 minutes on Week days 1, 3, and 5, then one infusion every 4 weeks

The randomization will use a 2:1 ratio (PRM-151: placebo). The randomization will also be stratified according to other treatments for IPF (subjects receiving pirfenidone or nintedanib and subjects with no other treatment for IPF).

After completion of study treatment through Week 24, all subjects may receive PRM-151 10 mg/kg IV infusion over 60 minutes Days 1, 3, and 5, then once every 4 weeks for an indefinite period of time in an open label study extension. Dosing will be administered on Days 1, 3, and 5 will be repeated once every 28 weeks during the extension.

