4.1.3. Open Label Post-Study Treatment Extension

4.1.4. After completing 24 weeks of treatment, all subjects will be offered the option to receive PRM-151 in an open-label PRM-151 treatment extension period for an indefinite period of time.. All subjects will receive PRM-151 10 mg/kg IV Days 1, 3, 5 then every 4 weeks in the extension. Dosing on days 1, 3 and 5 will be repeated every 28 weeks during the extension. PROs, PFTs, spirometry and 6MWT will be done every 4 weeks for the first 24 weeks and then every 12 weeks. DLco, FRC & TLC by nitrogen washout method will be done every 12 weeks. HRCT will be done at 1.5 years (Week 76) and 2.5 years (Week 128) on the same day as DLco and FRC & TLC by nitrogen washout. Subjects are allowed to begin treatment with, restart treatment with or increase the dose of pirfenidone or nintedanib after the week 28 visit have been performed

4.1.5.

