Special list of excluded medications	x	x	x	x	x	x	x	x	x	x	x	x	x	x	x	x
AE/SAE Assessment		x	x	x	x	x	x	x	x	x	x	x	x	x	x	x
ECG & Cytokines (ONLY in the event of an IRR after Baseline)		x	x	x	x	x	x	x	x	x	x	x	x	x	x	x
Efficacy Assessment[2]																
Patient Reported Outcomes; K-BILD & LCQ	x		x			x				x			x			x

Pulmonary Function Tests (PFTs)	x		x			x				x			x			x
DLCO[3]	x					x										
FRC & TLC by nitrogen washout method[4]	x					x										
HRCT (with spirometry at select sites)[5]						x										
6-minute walk test	x		x			x				x			x			x
Pregnancy test Each visit after V4 for all WOCBP	x															
Complete Blood Count	x		x			x				x			x			x
Chemistry, BUN/creatinine	x		x			x				x			x			x
Coagulation	x		x			x				x			x			x
Status of baseline genetic characteristics[6]																
Anti-pentraxin 2 antibodies (ADA), Pre-dose			x			x				x			x			x
Pentraxin-2 levels, Pre-dose			x			x				x			x			x
Exploratory laboratory assessments (optional)[7]																
PRM-151 dosing[8]		x	x	x	x	x	x	x	x	x	x	x	x	x	x	x

[1] Full physical exam at screening and an abbreviated physical exam thereafter.

[2] [REDACTED]
[REDACTED]

[8] Dosing on Days 1, 3, and 5 will be repeated every 28 weeks during the extension study. If the subject is not able to adhere to the original dosing schedule, the subject should be dosed as soon as possible within 2 weeks of the scheduled visit. If the subject dosing is >2 weeks sponsor should be consulted.

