2.3 Investigational plan

2.3.1 Study design and randomisation

This study is a Phase 2, randomized, double-blind, placebo controlled, pilot study designed to evaluate the efficacy and safety of PRM-151 administered through Week 24 to subjects with IPF. Subjects meeting the eligibility criteria for the study will be randomized with a 2:1 ratio to PRM-151 at a dose of 10 mg/kg every 4 weeks or placebo. The randomization will be stratified according to other treatments for IPF (with two strata: patients receiving either pirfenidone or nintedanib and patients with no other treatment for IPF, with a minimum of 25% of patients on no other treatment). Efficacy will be evaluated through pulmonary function tests (PFTs) including spirometry, Diffusion Capacity (DLCO) and Total Lung Capacity by Nitrogen washout method (TLC), quantitative imaging analysis of high resolution CT (HRCT), 6 minute walk test (6MWT), and patient reported outcomes (PROs).

Subjects will be evaluated for study eligibility during Screening within 4 weeks before enrollment and baseline assessments. Subjects who are determined to be eligible, based on screening assessments, will be enrolled in the study and randomly allocated to treatment with PRM-151 or placebo. Subjects will receive study drug treatment for at least 24 weeks.

Approximately 117 subjects will be randomly assigned on a 2:1 basis to treatment with PRM-151 or placebo, as follows:

- PRM-151 10 mg/kg IV infusion over 60 minutes days 1, 3, and 5 of week 0, then one infusion every 4 weeks

- Placebo IV infusion over 60 minutes on days 1, 3, and 5 of week 0, then one infusion every 4 weeks

After completion of study treatment through Week 24, all subjects may receive PRM-151 10 mg/kg IV infusion over 60 minutes Days 1, 3, and 5, then once every 4 weeks for up to an additional 96 weeks in an open label study extension. Dosing on Days 1, 3 and 5 will be repeated once every 24 weeks.

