5.1 General considerations

The statistical analyses are performed in accordance with the ICH E9 guideline and will be based on the pooled data from the individual study sites, unless otherwise stated. All available efficacy and safety data (according to definition provided in section 4) collected during the randomized phase of the study will be included in data listings and tabulations (i.e., OLE data will not be presented). Except for the analysis of the primary endpoint (see section 5.2.5.1 Primary efficacy analyses) and for selected secondary endpoints (see section 5.2.5.2 for details), all other analyses will be based on observed data only i.e., no missing data will be imputed.

The statistical analyses will be performed by an external Contract Research Organization (CRO), Venn Life Sciences, under the responsibility of the Sponsor.

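### The Day 1, 3 and 5 dosing series in the open-label extension repeats every 24 weeks in some current text and every 28 weeks in other current text

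*Protocol*

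**What the plan says.** The protocol gives two intervals for repeating the Day 1, 3 and 5 series in the extension.

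- Synopsis, extension paragraph just before Safety Assessments: "Dosing on Days 1, 3 and 5 will be repeated once every 24 weeks in the extension".
- Synopsis, Study Design: "Dosing on Days 1, 3 and 5 will be repeated once every 28 weeks".
- Section 4.1: the series "will be repeated once every 28 weeks during the extension".
- Section 4.1.3: "Dosing on days 1, 3 and 5 will be repeated every 28 weeks during the extension".
- Appendix A, footnote 8: "Dosing on Days 1, 3, and 5 will be repeated every 28 weeks during the extension study".

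The SAP gives the other interval from most of the protocol. Section 2.3.1 has "Dosing on Days 1, 3 and 5 will be repeated once every 24 weeks", and footnote 8 to the schedule in Section 2.3.3 also gives 24 weeks.

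The length of the extension is not settled either. The synopsis describes it as open-ended. The protocol's Study Duration section (numbered 4.1.6 in the body) caps total participation at 128 weeks and, in the same sentence, calls the extension indefinite. SAP Section 2.3.1 allows at most 96 further weeks, while the SAP schedule has an extension column running from Week 28 to Week 128.

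**The concern.** This is an operative dosing instruction in an extension offered to all subjects. A site that follows the synopsis paragraph and a site that follows Appendix A would bring patients in for the extra Day 3 and Day 5 infusions at different weeks. The protocol's tolerances do not absorb the difference. The visit window is ±3 days, and late dosing is allowed within 2 weeks before the sponsor has to be consulted (Section 6.2 and Appendix A, footnote 8), but the first repeats are 4 weeks apart.

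If sites diverged, exposure in the extension would differ between patients for no planned reason. Safety data collected there would then come from two regimens.

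**Working it through.** No power or sample-size formula applies. The check is schedule arithmetic.

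**Inputs.** The extension series starts at Week 28, where Appendix A has both a Day 1 column and a Days 3, 5 column. There is one infusion every 4 weeks, and each series adds two infusions (Days 3 and 5). The stated intervals are 24 and 28 weeks. The horizon is Week 128, the last visit named for extension HRCT in Section 4.1.3.

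**Appendix A against its own footnote.** The series columns stand at Weeks 28, 56 and 84. The gaps are 56 − 28 = 28 and 84 − 56 = 28, so the table agrees with its footnote 8. Under a 24-week interval the repeats would fall at Weeks 52, 76 and 100. The table shows those weeks as ordinary single-dose visits.

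**Series and infusions, Week 28 to Week 128.** Four-weekly visits: (128 − 28)/4 + 1 = 26. Total infusions = 26 + 2 × number of series.

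| Interval | Series weeks | Series | Infusions |
|---|---|---|---|
| 24 weeks | 28, 52, 76, 100, 124 | 5 | 26 + 2 × 5 = 36 |
| 28 weeks | 28, 56, 84, 112 | 4 | 26 + 2 × 4 = 34 |

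The difference is two infusions, and 36/34 = 1.059, or about 6%. After Week 28 the two lists share no week up to Week 128. They first meet again 168 weeks into the extension (7 × 24 = 6 × 28).

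**Dependence on the horizon.** In extension weeks (Week 28 = 0), series start at 0, 24, 48, 72 and 96 under one rule and at 0, 28, 56 and 84 under the other. Series started so far:

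| Extension weeks | 24-week rule | 28-week rule |
|---|---|---|
| 0–23 | 1 | 1 |
| 24–27 | 2 | 1 |
| 28–47 | 2 | 2 |
| 48–55 | 3 | 2 |
| 56–71 | 3 | 3 |
| 72–83 | 4 | 3 |
| 84–95 | 4 | 4 |
| 96–100 | 5 | 4 |

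**Timing at the Week 128 assessments.** The latest series would have started 128 − 124 = 4 weeks earlier under one rule and 128 − 112 = 16 weeks earlier under the other.

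**Extension length.** Ninety-six weeks after Week 28 is Week 124. Ninety-six weeks after Week 24 is Week 120. The SAP's own column from Week 28 to Week 128 spans 100 weeks. The fifth series under the 24-week rule falls at Week 124, so whether it is given at all depends on which length applies. The two inconsistencies therefore have to be settled together.

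**The case against.** The conflict is lopsided. Within the protocol a single sentence says 24 weeks; four places say 28, and the Appendix A columns are laid out accordingly. The other 24-week statements are in the SAP, in its summary of the protocol, and sites do not dose from a SAP. Site staff are likely to work from the visit table, which shows only one interval. Nothing in the documents indicates that any site departed from it.

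The analysis consequence is also limited. SAP Section 5.1 states that "OLE data will not be presented", Section 4.2.1 restricts the safety analysis to events before the first extension dose, and Section 2.3.3 treats Week 28 as the end of study. Finally, the two-infusion gap depends on the horizon: the counts are equal for long stretches, and a patient who leaves before extension week 24 is unaffected.

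All of this is correct and bounds the problem. It makes divergent dosing less likely and takes the planned analyses out of reach. It does not remove the contradiction: the synopsis is part of the protocol, the documents do not say which passage prevails, and the number of passages on each side does not establish which interval was intended. Equal counts at some horizons do not mean equal timing either, because the dates differ from the first repeat onwards.

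**Conclusion.** The concern holds. Current protocol text contradicts itself on the repeat interval, within the synopsis and between the synopsis and the body, and the SAP contradicts the protocol body. The first repeat differs by 4 weeks. Up to Week 128 the difference is one series, or two 10 mg/kg infusions, and it is zero at some intermediate horizons. This assumes that the first extension series is at Week 28, that no doses are missed and that the patient remains to Week 128. The conflict over extension length is also real.

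The reach is confined to conduct of the extension and any later reporting of its data. The Week 28 primary endpoint, the type I error rate, the power and the analyses in this SAP do not depend on the interval. It should still be corrected because it is an instruction on dosing. This review takes no position on which interval or length is right.

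**What to change.** The sponsor should state one repeat interval and one extension length, then bring these places into line:

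- Protocol synopsis: Study Design, Study Duration and the extension paragraph.
- Protocol Sections 4.1 and 4.1.3, and the Study Duration section.
- Appendix A: the series columns and footnote 8.
- SAP Section 2.3.1, and the extension column and footnote 8 of the schedule in Section 2.3.3.

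If patients have already entered the extension, record the weeks at which each actually received the Day 3 and Day 5 infusions, so that any later extension report can describe exposure as given.

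The cost is a protocol amendment or clarification letter to sites and a wording change in the SAP. No sample size, endpoint or planned analysis changes.
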